Nutrition claims on fruit drink packages are also very common. A 2014 report found that 100% of children's fruit drinks contain nutrition-related messages and 88% of other fruit drinks contain nutrition-related messages.¹⁶ Nutrition claims can be problematic because a claim on a single nutrient can lead consumers to mistakenly infer that the whole product is healthy, regardless of its overall nutritional profile (i.e., the "health halo effect"), and increase intentions to purchase the product.¹⁷⁻¹⁹ Nutrition claims also reduce the likelihood consumers will seek additional nutritional information (e.g., the nutrition facts panel on the back of the package).^{17, 20} One study found that parents were more likely to choose an unhealthy product if it included a nutrition claim,²¹ but this study focused only on sweetened milks, snacks, and processed foods. To our knowledge, no studies have examined the effect of nutrition claims on parents' choice of fruit drinks for their child.

Furthermore, there has been little research on the effects of specific claim types on fruit drinks, which is important for informing emergent policies at the Food and Drug Administration (FDA), who has regulatory authority over claims. For example, the FDA has recently announced plans to formally define "natural" claims,²² which appear on 50% of fruit drinks.¹⁶ Despite evidence from tobacco showing that natural claims reduce perceptions of a product's health harms and increase purchasing intentions,²³⁻²⁶ there is little evidence on whether these claims impact perceptions or purchases of fruit drinks. For example, "natural" claims could lead parents to believe that a fruit drink has nothing added (when in fact, sweeteners have been added) or reduce their perception of the disease risks associated with drinking SSBs. Research on this topic is urgently needed to inform the FDA's new definition of "natural" claims.

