5. Self-identify as non-Hispanic white, non-Hispanic Black, or Hispanic any race
6. Panel member on CloudResearch and/or Kantar

STUDY PROCEDURES (what will be done)

Study Steps

Panel Companies will reach out to panel members about this research study. If interested, panel members will complete a screener in Qualtrics to see if they are eligible. If they are not eligible, panel members will be redirected to a termination page indicating they are not eligible to participate. If they are eligible, panel members will be redirected to a consent form. If they agree to the consent form, they will acknowledge their consent by clicking an arrow to proceed to the study.

Qualtrics will randomize the participant to one of the twelve study arms and redirect the participant to iShoppe. In iShoppe the participant will be instructed to shop for their child who is between 1-5 years old. If they have more than one child aged 1-5, they will be instructed to think about the child who had their birthday most recently. They will then be instructed to select two beverages for their child. They will compare the two beverage options for each selection task (grape fruit drink vs. 100% grape fruit juice; apple fruit drink vs. water) and choose one of each. Once they have selected the two beverages, they will be instructed to select a granola snack (control snack with no label vs. experimental snack with label). Once all three products are in the participants' shopping basket, iShoppe will then redirect them to another Qualtrics survey. In the Qualtrics survey, participants will answer questions about their perceptions about and reactions to the fruit drinks and snack, as well as standard demographic questions (see measurements section for more detail). Upon completing the survey, participants will be redirected to a termination link where they will receive an incentive in a type and amount set by the panel company.

Subject Completion/ Withdrawal procedures

A study participant is determined to have completed the study when they have finished and exited the study survey. To withdraw their data from the study, a participant would have to contact the study team or the university IRB.

Screen failure procedures

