### **Analyses**

We will report descriptive results for all outcomes (i.e., means and proportions by group). In all models, the predictor will be a dummy variable indicating whether the participant was randomized to one of the three intervention nutrition claim conditions. For predictions with Likert-style outcomes, we will run linear regression models, one for each outcome. We will examine skewness of the residuals and run ordinal models in sensitivity analyses if residuals

are skewed, retaining the linear models if the pattern of results does not change. For predictions with dichotomous outcomes, we will use the same approach except with logistic regression. We will use the margins command in Stata for significance testing of control vs. each claim separately, as well as each claim compared to the other claims.

We will also report results when controlling for any participant demographic characteristics (including random assignment to two experiments conducted after the primary outcome, but before measurement of some of the secondary outcomes) found to be unbalanced across treatment arms in balance tests, if these results differ substantively from unadjusted results (i.e., changes in statistical significance or direction of effect).

We will examine whether the following participant characteristics moderate the effect claims on the primary outcome:

- a) Age of child shopping for (in years);
- b) Gender of parent (man vs. woman);
- c) Gender of child (boy vs. girl);
- d) Race/ethnicity of parent (White non-Hispanic vs. Black non-Hispanic vs. Hispanic);
- e) Low educational attainment (dichotomized based on sample distribution);
- f) Household income (dichotomized based on sample distribution);
- g) Child's frequency of consuming fruit drinks (above vs. at or below the sample median);
- h) Time spent looking at Nutrition Facts Panel of the beverage;
- i) Seeking vitamin C since COVID-19 pandemic

To test whether these characteristics moderate the effect of claims on selection, we will fit a series of logistic regressions models (one for each potential moderator), with trial arm, the moderator, and their interaction as predictors. We will probe significant interactions by calculating the marginal effect of nutrition claims on the outcome at different levels of the moderating variable.

We will use a critical alpha of 0.05 and statistical tests will be two-tailed. We will correct for multiple comparisons.

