### Analyses

We will report descriptive results for all outcomes (i.e., means and proportions by group). In all models, the predictor will be a dummy variable indicating whether the participant was randomized to one of the two warning message conditions. For predictions with Likert-style outcomes, we will run linear regression models, one for each outcome. We will examine skewness of the residuals and run ordinal models in sensitivity analyses if residuals are skewed, retaining the linear models if the pattern of results does not change. For predictions with dichotomous outcomes, we will use the same approach except with logistic regression. We will use the margins command in Stata for significance testing of control vs. each warning message separately, as well as each warning message compared to each other. We will also report results when controlling for any participant demographic characteristics (including random assignment to experiments conducted before the primary outcomes) found to be unbalanced across treatment arms in balance tests, if these results differ substantively from unadjusted results (i.e., changes in statistical significance or direction of effect).

We will examine whether the following participant characteristics moderate the effect claims on the primary outcome:

- a) Age of child shopping for (in years);
- b) Gender of parent (man vs. woman);
- c) Gender of child (boy vs. girl);
- d) Race/ethnicity of parent (White non-Hispanic vs. Black non-Hispanic vs. Hispanic);
- e) Low educational attainment (dichotomized based on sample distribution);
- f) Household income (dichotomized based on sample distribution);
- g) Time spent looking at Nutrition Facts Panel of the snack;

To test whether these characteristics moderate the effect of warning messages on selection, we will fit a series of logistic regressions models (one for each potential moderator), with trial arm, the moderator, and their interaction as predictors. We will probe significant interactions by calculating the marginal effect of sugar warnings on the outcome at different levels of the moderating variable.

We will use a critical alpha of 0.05 and statistical tests will be two-tailed. We will correct for multiple comparisons.

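### Nutrition Facts Panel viewing time arises after randomisation but is tested as a participant characteristic that moderates the label effect, so that interaction is not a randomised contrast and can be biased

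*SAP*

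**What the plan says.** The Task 1 moderator list (SAP, Task 1, Analyses) opens: "We will examine whether the following participant characteristics moderate the effect claims on the primary outcome". Item h is "Time spent looking at Nutrition Facts Panel of the beverage". The Task 2 list has "Time spent looking at Nutrition Facts Panel of the snack" as item g. Both items recur in the protocol under Statistical Methods. They stand beside child age, parent gender, race/ethnicity, education and income, and are handled in the same way: one logistic regression per moderator, "with trial arm, the moderator, and their interaction as predictors". The follow-up rule for Task 1, with a matching rule for Task 2, is: "We will probe significant interactions by calculating the marginal effect of nutrition claims on the outcome at different levels of the moderating variable".

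The order of events is in the protocol, Study Procedures, Study Steps: "Qualtrics will randomize the participant to one of the twelve study arms and redirect the participant to iShoppe". Shopping comes after that.

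The protocol's Background and Rationale (Task 1) also states: "Nutrition claims also reduce the likelihood consumers will seek additional nutritional information". It names the nutrition facts panel as the example. Neither document marks the viewing-time items as post-randomisation, mediating or exploratory.

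**The concern.** A moderator analysis keeps the protection of randomisation only if the moderator is fixed before assignment, or at least is not affected by it. Viewing time for a study product's panel cannot exist until the participant has been assigned and shown the product. For Task 1, the protocol's own rationale makes it an expected consequence of the claim.

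If the label shifts viewing, and viewing shares causes with choice (health-consciousness, for example), then panel readers in the claim arm and panel readers in the control arm are different kinds of parents. Comparing them mixes the label effect with that difference. If viewing itself alters choice, holding it fixed also leaves out the part of the label effect that runs through viewing.

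Under some forms of this shift, a paper could report that claims deter panel readers from the fruit drink when claims change nobody's choice and nothing is moderated. The protocol wants its results to inform regulation and legal action, where such a statement could be read causally.

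**Working it through.** **No planned figure to reproduce.** The only power statement (about 2,170 participants, f = 0.06) does not bear on this point.

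**Why the contrast is not randomised.** Let A be arm, M viewing, U a common cause and Y choice. The plan probes

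E[Y | A=1, M=m] − E[Y | A=0, M=m].

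If the label has no effect on choice, and viewing has none either, each term is the average of P(Y=1 | U=u) over the density f(u | A=a, M=m), which is proportional to P(M=m | A=a, u) × f(u). Randomisation makes f(u) the same in both arms. It does not make P(M=m | A=a, u) the same. The probed difference is guaranteed to be zero only if the label does not shift M, or if U does not drive Y.

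**Simulation inputs (assumed, since the documents give none).**
- U is standard normal; log-odds of reading the panel = U + label shift.
- Log-odds of choosing the higher-sugar product = g × U; no label effect on choice.
- A selective shift applies only when U < 0.
- The model is logistic with arm, reading and their interaction, as in the SAP; 4,000 runs per scenario.
- Task 1: 2,175/4 = 543 per arm, analysed as 543 v 543 and as 543 v 1,629 (3 × 543). Task 2: 2,175/3 = 725 per arm, analysed as 725 v 725 and as 725 v 1,450 (2 × 725).
- Monte Carlo error is about ±0.7 points at 5% and ±1.4 points at 30%.

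**Task 1 results** (true label effect 0; percentage points, pp):

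| Shift in reading (log-odds) | g | Apparent effect, non-readers / readers | Interaction rejects at 0.05 |
|---|---|---|---|
| None | −1 | 0 / 0 | 5.1–5.7% |
| Uniform −0.7 (50% to 36% read) | −1 | −2.3 to −2.5 in each | 4.9–5.6% |
| Selective −0.7 (50% to 44%) | −1 | +0.5 / −3.3 | 10.0–13.5% |
| Selective −1.4 (50% to 39%) | −1 | +1.0 / −6.2 | 21.7–31.5% |
| Selective −0.7 to −1.4 | −0.5 | strata differ by 2 to 4 | 5.9–11.6% |
| Selective −1.4 | 0 | 0 / 0 | 4.8–5.2% |

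In the two selective rows with g = −1, the strata differ by 0.5 + 3.3 = 3.8 pp and 1.0 + 6.2 = 7.2 pp. With Bonferroni over nine moderators (0.05/9 = 0.56%), those two rows reject 1.7–9.7%. Replacing read/not read with log(1 + seconds) gives rejection of 10.3–32.7% under the selective shifts and 5.7–5.8% with no shift.

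**Task 2 results** (g = −1; direction of any shift unknown). Selective lowering of reading by 0.7 to 1.4 makes the strata differ by 4 to 7 pp, with rejection of 11.3–34.4%. Selective raising by 0.7 to 1.4 makes them differ by 5 to 10 pp the other way, with rejection of 14.4–57.6%. With Bonferroni over seven (0.05/7 = 0.71%), these fall to about 3–15% and 4–29%.

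**A second model with a different structure.** This uses 2,170 participants, any claim v control, and a latent tendency to look that the claim lowers by the same amount in everyone, with viewing time floored at zero.
- If the share who look falls from 40% to 30%, the test rejects 6.6% (trait log-odds for choice of 0.4 in size) to 10.6% (0.8).
- If it falls from 40% to 20%, the test rejects 11.1% to about 28–30%.
- If viewing is instead normal and shifted uniformly, the test stays near 4%. The probed effect is then about −6.4 pp at both low and high viewing time, against a true value of 0.

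**Primary contrast.** The label comparison that does not condition on viewing stayed within 0.1 pp of zero in every scenario of the first model quoted here.

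**The case against.** The strongest reply is that the larger rates rest on an assumed shape. The background says only that claims reduce information-seeking, not that they do so only in less health-conscious parents. Under a uniform shift in read/not read, the interaction test stays near 5%, and since only significant interactions are probed, the biased stratum effects would rarely be reported. This stands in part: no particular rate can be claimed. But a uniform shift does not guarantee a safe test, since with a floor at zero seconds it also inflated rejection.

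Second, the plan corrects for multiple comparisons. That lowers the rates, as shown, but it controls chance error and not bias: 1.7–9.7% is still above 0.56%. The plan names neither method nor family, so Bonferroni is itself an assumption.

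Third, effect sizes among significant results should not be attributed to bias alone. In the selective Task 1 cases with g = −1, significant runs average +3.5 to +4.8 pp in non-readers and −7 to −11 pp in readers. Yet with no bias at all, significant runs already show strata about 11–14 pp apart, against about 12–15 pp in the selective cases. This stands: bias mainly makes significance more frequent and its direction systematic.

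Fourth, for Task 2 nothing in the documents says that warnings change viewing, so only the timing argument applies. This stands.

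Fifth, the scope is small: one of nine Task 1 and one of seven Task 2 moderators, and none of the 12 Task 1 or 15 Task 2 predictions concerns moderation. This also stands and limits the weight of the point.

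**Conclusion.** The concern holds. Viewing time is a post-randomisation variable treated as a participant characteristic, and the resulting interaction test and level-specific effects are not randomised contrasts. The documents settle this for both tasks. For Task 1 they also supply a reason to expect the label to shift viewing.

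Whether bias occurs, and how large it is, cannot be found from the documents. It needs both a label-induced shift in viewing and a shared cause of viewing and choice; a separate effect of viewing on choice would add the omitted-pathway problem. Under the assumed values, the result ranges from no bias, through biased stratum effects with a near-nominal test, to Task 1 rejection of 10–31% uncorrected. The Task 2 figures are the most speculative.

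The primary label comparisons, sample size, alpha and pre-randomisation moderators are unaffected. This is a worthwhile and inexpensive correction to a secondary analysis, not a threat to the trial's main result.

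**What to change.** Delete viewing time from the moderator lists in four places: SAP Task 1 (item h), SAP Task 2 (item g), and the matching items in the protocol's Statistical Methods for each task. In its place:

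- Report viewing by arm as a process outcome: the share with any viewing, and the time spent.
- State how viewing time is recorded and which of the displayed products it refers to; the documents do not say.
- If its role is of interest, keep an exploratory mediation analysis, or a descriptive table of choice by arm and viewing, with assumptions stated and no claim that viewing moderates the label effect.

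The cost is wording only. The viewing-time data are already needed for the planned analysis. The downside is that one pre-specified moderator analysis per task becomes exploratory.

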## **Task 2**

### **Predictions**

The aim of Task 2 is to examine how sugar warnings on granola snack packaging influence US parents' selections, perceptions, and reactions. We have the following predictions:

1. Parents who see a warning message on a high-sugar granola snack will be more likely to select the lower-sugar snack than those who see a control message.
2. Sugar warnings will lead to lower perceived appeal of high-sugar granola snacks.
3. Sugar warnings will lead to lower intent to give a high-sugar granola snack to one's child.
4. Sugar warnings will lead to lower intent to purchase a high-sugar granola snack.
5. Sugar warnings will lead to lower intent to consume a high-sugar granola snack.
6. Sugar warnings will lead to lower perceptions of healthfulness of a high-sugar snack for one's child to consume.
7. Parents who view sugar warnings will rate them as having higher perceived message effectiveness than parents who view the control label.

8. Parents who view sugar warnings will be more likely to talk about them with others in the next week than parents who view the control label.
9. Parents who view sugar warnings will be more likely to report that they learned something new from the label than parents who view the control label.
10. Parents who view sugar warnings will rate them as grabbing their attention more than parents who view the control label.
11. Parents who view sugar warnings will rate them as making them feel scared more than parents who view the control label.
12. Parents who view sugar warnings will rate them as making them think about the health problems caused by eating the snack more than parents who view the control label.
13. Sugar warnings will lead to greater accuracy in identifying which of two snacks is higher in added sugar.
14. Sugar warnings will lead to greater accuracy in identifying which of two snacks is healthier for one's child to consume.
15. Sugar warnings will lead to lower intentions to buy the higher-sugar snack for one's child (vs. the lower sugar snack).

### Analyses

We will report descriptive results for all outcomes (i.e., means and proportions by group). In all models, the predictor will be a dummy variable indicating whether the participant was randomized to one of the two warning message conditions. For predictions with Likert-style outcomes, we will run linear regression models, one for each outcome. We will examine skewness of the residuals and run ordinal models in sensitivity analyses if residuals are skewed, retaining the linear models if the pattern of results does not change. For predictions with dichotomous outcomes, we will use the same approach except with logistic regression. We will use the margins command in Stata for significance testing of control vs. each warning message separately, as well as each warning message compared to each other. We will also report results when controlling for any participant demographic characteristics (including random assignment to experiments conducted before the primary outcomes) found to be unbalanced across treatment arms in balance tests, if these results differ substantively from unadjusted results (i.e., changes in statistical significance or direction of effect).

We will examine whether the following participant characteristics moderate the effect claims on the primary outcome:

- a) Age of child shopping for (in years);
- b) Gender of parent (man vs. woman);
- c) Gender of child (boy vs. girl);
- d) Race/ethnicity of parent (White non-Hispanic vs. Black non-Hispanic vs. Hispanic);
- e) Low educational attainment (dichotomized based on sample distribution);
- f) Household income (dichotomized based on sample distribution);
- g) Time spent looking at Nutrition Facts Panel of the snack;

To test whether these characteristics moderate the effect of warning messages on selection, we will fit a series of logistic regressions models (one for each potential moderator), with trial arm, the moderator, and their interaction as predictors. We will probe significant interactions by calculating the marginal effect of sugar warnings on the outcome at different levels of the moderating variable.

We will use a critical alpha of 0.05 and statistical tests will be two-tailed. We will correct for multiple comparisons.
